5.1.3 Primary Endpoints

- (a) HIV-1 antibody seroconversion
- (b) ELISPOT measurement of HIV-1 peptide-specific T lymphocytes
- (c) HLA-Class I MHC alleles

5.2 Secondary Outcomes

5.2.1 Secondary Objectives (a) To determine if the detection of an HIV-1 -specific immune response in exposed uninfected individuals, correlates with the HIV-1 viral set point in individuals that subsequently become HIV-1 infected.

For HIV-1 exposed subjects that subsequently seroconvert, viral load measurements will be taken to determine if subjects with detectable ELISPOT responses to the gag protein had lower viral set point than those HIV-1 exposed subjects that had no detectable immune response to the gag protein.

5.2.2 Secondary Objectives (b) To compare the epitope specificity of the HIV-1 -specific immune response of exposeduninfected individuals with that of their recently infected partners.

In cases where positive responses are detected in the initial screen of the ELISPOT assay, additional assays will be performed on stored specimens to determine the phenotype of the responding cell, epitope specificity and MHC restriction. ELISPOT responses to HIV-1 gag peptides in recently infected subjects and their exposed uninfected partners will be compared to see in the same sub-set of epitopes is recognized in those discordant couples that share HLA alleles.

5.2.3 Secondary Objectives (c)

To assess the feasibility of establishing a prospective cohort of recently infected individuals and their primary sexual partners for participation in HPTN HIV-1 prevention trials of discordant couples.

This laboratory study will provide an opportunity to assess the feasibility of establishing and following cohorts of recently infected individuals and their sexual partners for future HPTN trials. Therefore enrollment and retention rates will be enumerated and evaluated for the Pune site.

5.2.4 Secondary Endpoints

- (a) Median HIV-1 viral load between 6 and 12 months after estimated time of infection, for participants that HIV-1 seroconvert.
- (b) HLA restriction and minimal peptide sequence of responding T lymphocytes from exposed uninfected participants.
- (c) Enrollment and retention of study participants and their acutely infected partners enrolled in the 034A HPTN Early Infection Laboratory Sub-study.

6.0. Data Collection

6.1 Data Forms

Data will be collected on standardized forms to be outlined in the site-specific procedures manual. An appropriate system for data transfer from the sites to the HPTN Core Laboratory and for central data management, quality assurance and analysis will be developed and utilized. A data and care report forms flow chart will be included in the study specific procedures manual along with procedures for data collection, transfer, and management.

6.2 Record Storage and Archive

The study site principal investigator and laboratory personnel will maintain all source documents used to complete case report forms including laboratory requisitions and reports, documentation of referrals, and progress notes. Specimens will be tracked using the Laboratory Data Management System (LDMS). All data collection forms and source records must be kept in locked files in a secure area. All study documents with participant identifying information including locator information and informed consent forms must be kept in locked files in a secure area apart from all other study documents. Study records must be available at all times for review by FHI, the study sponsor (NIAID) or their agents.

6.3 Statistical Considerations and Sample Size Calculations

Based upon assumptions outlined below for each of the two primary objectives, the target samples size for this study is a minimum of 20 subjects who are HIV-1 -exposed uninfected individuals with recently infected partners. For both primary objectives, frequency of HIV-1 infection will be an outcome measure. Patients will be divided into an infected and uninfected

cohort and compared with respect to the presence or absence of any prior detectable immune response as measured by Elispot.

6.3.1 Primary Objectives (a). Gag-specific ELISPOT Response vs. subsequent HIV-1 Infection.

For the purposes of comparing ELISPOT response to incidence of infections, gag-specific ELISPOT responses will be scored as positive or negative. As outlined in Appendix C, all experiments will be performed in duplicate wells. The IFN- γ -expressing spots will be calculated as the number of spots per 10⁵ stimulated PBMCs. Results will be expressed as net peptide-specific IFN- γ spots / 10⁵ PBMC. A positive peptide-specific response (responders) will be defined as a mean of greater than 5 spots above the mean spots of the mock-stimulated PBMC. Study participants will be expected to have multiple ELISPOT assays within the first 12 months of follow-up (See Appendix A). For the purpose of the sample size calculation, our initial analysis will compare HIV-infection with a positive response to any gag peptide, at any time point within 12 months since enrollment. Separate and similar analyses will be performed for recognition of HIV-1 subtype B gag and non-B gag peptides. Assuming a 20% seroconversion rate among the exposed uninfected cohort resulting in 20 acutely infected patients, we would have 80% power to detect at least a 25% difference in the proportion of individuals who elicit a gag immune response between the two groups (infected and uninfected).

Difference in proportion of patients with	Total sample size (unequal arms assuming
gag response	20% seroconversion rate)
20%	238
25%	138
30%	86

6.3.2 Correlation of HLA allelic expression with risk of subsequent infection.

The proportion of individuals with certain HLA Class I alleles will be compared between infected and uninfected individuals. Using HLA A2 as an example (known to exhibit good immune response to gag), we posit that a higher percentage of this allele will be found in the uninfected cohort. Using a similar calculation to 6.3.1, we will have 80% power to detect at least a 25% difference in allelic frequency between the two groups.

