4.2 Enrollment

Enrollment will take place over the two years of the HPTN 034 protocol; participants will be followed for up to two years, if funding is available. The schedule for sample collection is outlined in Table 1. If it can be determined that participants were infected within the previous three months, samples would be drawn at enrollment, once a month for three months, and then every three months for up to two years. If participants have been infected for more than three months, and less then six months, specimens would be collected at enrollment, and every three

months for up to two years. Participants will be asked to provide a 40 ml blood sample (four EDTA vacutainer tubes, 10mls/tube), answer a short questionnaire and undergo a brief physical exam. PBMC and plasma will be stored on site for immunologic and virologic studies through the CL.

Study participants with recent HIV-1 infection will be also be strongly advised to refer their primary sexual partner(s) for HIV-1 screening and risk reduction counseling. Sexual partners of participants with recent HIV-1 infection who agree to HIV-1 screening will be determined to be either chronically HIV-1 infected of unknown duration, recently HIV-1 infected themselves, or HIV-1-uninfected. Those partners found to be recently HIV-1-infected will also be eligible for enrollment in this study. Partners found not to be HIV-1 infected will be eligible to enroll in a companion HPTN sub-study of exposed-uninfected partners (HPTN 034B).

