We, the Principal Investigators, agree to conduct this study in full accordance with the provisions of this protocol. I agree to maintain all study documentation for a minimum of five years from the end of the study, unless directed otherwise by the HPTN Coordinating and Operations Center (CORE). Publication of the results of this study will be governed by HPTN and DAIDS policies. Any presentation, abstract, or manuscript will be made available by the investigators to the HPTN Manuscript Review Committee and DAIDS for review prior to submission.

We have read and understand the information in this protocol and will ensure that all associates, colleagues, and employees assisting in the conduct of the study are informed about the obligations incurred by their contribution to the study.

Name of Principal Investigator		
Signature of Principal Investigator	Date	
Name of Principal Investigator		-
Signature of Principal Investigator	Date	

HPTN 034 B HPTN EXPOSED-UNINFECTED LABORATORY SUB-STUDY **PROTOCOL SUMMARY**

Design:	Laboratory Sub-study for HPTN 034
Study Sites/Population:	Adult men and women who have been identified as HIV-1 uninfected sexual partners of recently HIV-1 infected participants in the HPTN 034A sub-study
Study Duration:	The sub-study is designed to run for the duration of the entire HPTN 034 funding period. Participants will be continuously enrolled and followed for up to two years, as funding allows.
Primary Objectives:	 (a) To determine if the detection of an HIV-1 -specific immune response in exposed uninfected individuals correlates with risk of subsequent HIV-1 infection. (b) To determine if immunologic genetic characteristics of exposed uninfected individuals correlates with risk of subsequent HIV-1 infection.
Primary Endpoints	 (a) HIV-1 antibody seroconversion (b) ELISPOT measurement of HIV-1 peptide-specific T lymphocytes (c) HLA-Class I MHC alleles
Secondary Objectives:	 (a)To determine if the detection of an HIV-1 -specific immune response in exposed-uninfected individuals correlates with the HIV-1 viral set point in individuals that subsequently become HIV-1 infected. (b) To compare the epitope specificity of the HIV-1-specific immune response of exposed-uninfected individuals with that of their recently infected partners. (c) To assess the feasibility of establishing a prospective cohort of recently infected individuals and their primary sexual partners for participation in HPTN HIV-1 prevention trials of discordant couples.

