2.0 STUDY OBJECTIVES AND DESIGN

2.1 Primary Objectives

- To determine if the detection of an HIV-1 -specific immune response in exposed uninfected individuals correlates with risk of subsequent HIV-1 infection.
- To determine if immunologic genetic characteristics of exposed uninfected individuals correlates with risk of subsequent HIV-1 infection.

2.2 Secondary Objectives:

- To determine if the detection of an HIV-1 -specific immune response in exposed uninfected individuals correlates with the HIV-1 viral set point in individuals that subsequently become HIV-1 infected.
- To compare the epitope specificity of the HIV-1 -specific immune response of exposed-uninfected individuals with that of their recently infected partners.
- To assess the feasibility of establishing a prospective cohort of recently infected individuals and their primary sexual partners for participation in HPTN HIV-1 prevention trials of discordant couples.

2.3 Study Design:

This is a prospective cohort study to be conducted at NARI. NARI will implement the study in accordance with this protocol, however additional studies and collaborations may be incorporated into this study with approval from the Executive Committee. NARI will document study data using standard data collection forms to be submitted to the HPTN Statistical and Data Management Center (SDMC).

An estimated 10-15 individuals/year who qualify as HIV-1 -exposed uninfected are expected to be enrolled in this study. To maximize efficiency and to utilize established systems for screening and follow-up, individuals who themselves are HIV-1 negative, but who have recently infected partners will be recruited from the ongoing 034 HPTN trial. Enrollment will be offered to all participants in HPTN protocols who fulfill the enrollment inclusion/exclusion criteria. Individuals will necessarily have had a previously documented negative HIV-1 test that will be confirmed by HIV-1 RNA PCR. Appendix A (Table 1) reflects the clinical and laboratory specimens that will be collected at each visit. In this protocol, only samples from exposed-uninfected individuals will be collected. Samples from seropositive and seronegative individuals enrolled in the 034AHPTN Early HIV-1 Infection Study Laboroatory Sub-study will serve as comparative controls for the assays performed in the exposed-uninfected study.

3.0 Study Population:

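### 034B section 6.3 gives three sample sizes that do not agree (a target of at least 20, an implied 100, a table value of 138), and its 80% power is not available at the planned size

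*Supplement*

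**What the plan says.** All references are to the 034B sub-study unless marked otherwise.

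- **Target (6.3).** On assumptions to be listed for each primary objective, "the target samples size for this study is a minimum of 20 subjects who are HIV-1 -exposed uninfected individuals with recently infected partners".
- **Accrual (2.3).** "An estimated 10-15 individuals/year who qualify as HIV-1 -exposed uninfected are expected to be enrolled in this study". The Protocol Summary ties the duration to the HPTN 034 funding period and adds: "Participants will be continuously enrolled and followed for up to two years, as funding allows". The companion sub-study 034A says in its section 4.2: "Enrollment will take place over the two years of the HPTN 034 protocol".
- **Power, objective (a), gag response (6.3.1).** "Assuming a 20% seroconversion rate among the exposed uninfected cohort resulting in 20 acutely infected patients", and on that footing "we would have 80% power to detect at least a 25% difference in the proportion of individuals who elicit a gag immune response", comparing infected with uninfected participants.
- **Table (6.3.1).** Total sample sizes with unequal arms and 20% seroconversion: 238 for a 20% difference, 138 for 25%, 86 for 30%.
- **Power, objective (b), HLA alleles (6.3.2).** By a calculation described as similar to 6.3.1, "we will have 80% power to detect at least a 25% difference in allelic frequency between the two groups".

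Neither 6.3.1 nor 6.3.2 states the baseline response proportion or the significance level. 034A section 6.3.1 describes 034A as descriptive, says its sample is not expected to settle the primary endpoint, and assigns its 80% power to future data from several HPTN protocols. 034B section 6.3 has no such statement. The 2004 Letter of Amendment lists no change to 034B 6.3.

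**The concern.** A reader of 6.3 would take the target of 20 as the result of the calculation that follows it, and both primary objectives as having 80% power. The target, the power sentence and the table each imply a different study, and the smallest entry in the table (86) is more than four times the target.

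The risk lies in interpretation. If 034B finds no significant association between gag response or HLA type and later infection, a protocol that claims 80% power invites readers to treat that as evidence against protection. With a handful of infections it would be weak evidence either way.

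**Working it through.** **Inputs.** Target 20 (6.3); 10-15 enrolled per year (2.3); 20% seroconversion, 20 infected, 80% power and a 25-point difference (6.3.1); table totals 238/138/86 (6.3.1). Assumed: two-sided alpha 0.05, since 034B gives none and 034A uses p=0.05; and two years of enrolment, taken from 034A 4.2, which gives 20-30 participants.

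**Step 1: the sizes implied.**
- Target: 0.20 × 20 = 4 infections (0.20 × 30 = 6).
- Power sentence: 20 / 0.20 = 100 enrolled.
- Table, 25-point row: 0.20 × 138 = 27.6, about 28 infections.

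**Step 2: reproduce the table.** Two-proportion formula with pooled variance, no continuity correction, k = 4 uninfected per infected:

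n₁ = [1.96·√(p̄(1−p̄)(1+1/k)) + 0.8416·√(p₁(1−p₁) + p₂(1−p₂)/k)]² / d², total = 5·n₁, p̄ = (p₁ + k·p₂)/(k+1).

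A scan of baselines fits best at 60% in the infected group. For 60% v 85%, p̄ = 0.80:
- first term 1.96·√(0.16 × 1.25) = 0.8765
- second term 0.8416·√(0.24 + 0.1275/4) = 0.4388
- n₁ = (1.3153)² / 0.0625 = 27.68, total 138.4.

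The three rows (60% v 80/85/90%) give 238.5 / 138.4 / 84.7 against the printed 238 / 138 / 86. The mirror image, 40% v 20/15/10%, gives the same totals.

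**Step 3: power at each size, 60% v 85%.** Normal approximation: Φ{[d·√n₁ − 0.8765] / √0.271875}. For n₁ = 4: (0.25 × 2 − 0.8765) / 0.5214 = −0.722, so 23.5%. Fisher power is by full enumeration.

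| Enrolled | Infected v uninfected | Normal | Fisher |
|---|---|---|---|
| 20 | 4 v 16 | 23.5% | 13.7% |
| 30 | 6 v 24 | 30.6% | 24.3% |
| 100 | 20 v 80 | 67.8% | 63.1% |
| 138 | 28 v 110 | 80.2% | 76.3% |

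**Step 4: other baselines.** The baseline is inferred, so every 25-point pair was scanned, with the infected group lower or higher. The most favourable cases lie at the extremes, where one group is at 0% or 100%:
- N=20: at most about 52% (normal) or 26% (Fisher).
- N=30: at most about 62% (normal) or 47% (Fisher).

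Mid-range baselines are worse: 35% v 60% gives 7% (N=20) and 12% (N=30) by Fisher.

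**The case against.** **The target is a minimum.** True, and 30 is not a stated 034B target; it depends on borrowing the two-year enrolment period from 034A. The length of the funding period is not given. A third year at 15 per year would make 45 participants and 9 infections, with power of about 40% (normal) or 35% (Fisher) at 60% v 85%. At 10-15 per year, 138 would take roughly 9 to 14 years (138/15 = 9.2; 138/10 = 13.8).

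**The claim for objective (a) is conditional.** Also true: 6.3.1 says what power would follow from 20 infections, and does not say that 20 enrolled participants give 80%. But the target cannot supply 20 infections at 20%, and 6.3.2 makes its claim without the condition.

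**Sentence and table might use different baselines.** With 20 v 80, 70% v 95% gives 84% (normal) or 83% (Fisher), so 20 infections can suffice for some baseline. The conflict rests on the natural reading that both describe one calculation. This shows why the baseline must be stated.

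**034B is a laboratory sub-study with a capacity-building and network purpose.** Its rationale speaks of a repository and of cohorts across the network, so the larger numbers may have been meant for pooled data. That mitigates the point, but 6.3 does not say it, whereas 034A does.

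**Stronger readings that the documents do not support.** A reader might infer that power is at most 31%, or that a null result is nearly certain. The first fails because the baseline is unstated and extreme baselines give more. The second fails because, at 60% v 85%, the chance of missing a real 25-point difference is 69-86%: likely, not certain.

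**Conclusion.** The point stands as an internal inconsistency with a power claim that the planned size does not deliver. The target, the power sentence and the table of 034B 6.3 imply 20, 100 and 138 participants, or about 4, 20 and 28 infections. That mismatch follows from the plan's own figures and needs no assumption beyond reading sentence and table as one calculation.

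The power figures rest on a two-sided 5% test and an inferred baseline of 60% v 85%: 14-24% at 20, 24-31% at 30 and 63-68% at 100 (Fisher to normal). The conclusion that power stays under 80% at 20-30 participants does not depend on that baseline. For a 25-point difference in allele frequency the same arithmetic applies to objective (b). The parent study's primary endpoints, HIV incidence and retention, are not affected.

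**What to change.** In 034B 6.3.1 and 6.3.2:

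1. Remove the 80% power claim for 034B at its planned size.
2. Describe 034B as descriptive, as 034A does. Give the expected number of infections (about 4 at 20 participants, 6 at 30 if two years' accrual is assumed) and report estimates with exact confidence intervals.
3. Attach 80% power only to a named pooled analysis of about 138 participants with about 28 infections.
4. Make the power sentence agree with the table: about 28 infections in place of 20 if both use the baseline inferred here, or the baseline under which 20 is right.
5. State the baseline proportion and alpha, for both objectives.

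The change is to wording only. The stated power becomes less favourable; no extra participants, visits or assays are needed.

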3.1 Inclusion Criteria for HEPS Subjects

Eligible subjects would include individuals from the following population:

• HIV-1 uninfected partners of those enrolled in the 034A HPTN Early HIV-1 Infection Laboratory Sub-study.

All of the following must be fulfilled:

- Willing and able to provide informed consent
- \bullet > 18 years of age
- Willing to permit phlebotomy of four tubes of blood every three months for 24 months

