published in the current literature, and the compendium of sequence data from the HIV-1 molecular database at the Los Alamos National Laboratory (53).

Based upon the data from prior studies and an initial assessment of the logistical limitations of initiating this type study at multiple HPTU, this proposal will initially focus on measurement of HIV-1 gag-specific ELISPOT responses utilizing a matrix format of pools of overlapping HIV-1 gag peptides(54-57). NARI will initially be provided with a set of HIV-1 subtype C gag peptides. Based upon this initial analysis of the gag-specific responses and upon data from other ongoing studies, we propose to consider expanding this analysis to include assessment of other HIV-1 antigens, including env, pol, nef and tat. The details of the proposed consensus ELISPOT assay with gag peptides are provided in Appendix C. ELISPOT measurements will be made as early and frequently as possible after initial identification of infection. The visit schedule is outlined in Appendix A. The need for these frequent blood draws is comes from data that suggests that the epitope recognition seen in exposed uninfected individuals may be transient and variable.

Based upon the analysis of the ELISPOT data, a decision will be made by a consensus of the protocol team, which includes NARI site investigators and investigators outside of the HPTN, about expanding the analyses to other immunological assays (e.g. tetramer, intracellular flow cytometric assays, co-receptor genetic analysis), other antigens (e.g. nef, pol, env, tat) and other critical scientific questions. New information is continuously being generated that impacts our understanding of events critical to HIV-1 transmission and pathogenesis. To optimize the relevance of this study to the HPTN, the protocol team must include outside expertise and must stay informed about the latest information that might suggest modifications in the specifics of the laboratory assays utilized for this protocol. This protocol must also facilitate and be coordinated with ongoing, related laboratory studies at participating HPTUs, as well as with outside collaborators. The science in this field moves quickly and this laboratory protocol must remain dynamic, flexible, informed and collaborative to optimize this important scientific opportunity.

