5.0 Evaluation of Outcomes

5.1 Primary Outcomes

Following the successful implementation of immunologic (ELISPOT) and virologic (viral load measurements) assays at NARI (See quality control and training details above), this project will collect data to address the two stated primary objectives.

5.1.1.Primary Objectives (a).

To determine if the detection of an HIV-1 -specific immune response in exposed uninfected individuals, correlates with risk of subsequent HIV-1 infection.

The initial research hypothesis for this objective, based upon a few prior studies of HIV-1 exposed, uninfected individuals, is that exposed uninfected individuals with CD8mediated recognition of HIV-1 -gag epitopes will demonstrate a lower risk of subsequent HIV-1 infection, compared with exposed individuals that do not recognize HIV-1 gag epitopes. A further hypothesis is that this correlation will be demonstrated in exposed uninfected individuals, who are exposed to recently infected individuals infected with different strains of HIV-1. The primary outcome measures for this analysis will be subsequent HIV-1 infection within the first 2 years of follow-up, and demonstration of an HIV-1 gag-specific response measured in an ELISPOT assay. Based upon this initial analysis of gag-responses and upon data from other ongoing studies, we propose to consider expanding this ELISPOT analysis to include assessment of recognition of other HIV-1 antigens, including env, nef and tat.

5.1.2. Primary Objectives (b).

To determine if immunologic genetic characteristics of exposed uninfected individuals correlates with risk of subsequent HIV-1 infection, across diverse populations.

The initial research hypothesis for this objective, based upon prior studies in a few countries demonstrating that certain HLA class I alleles may be associated with a lower risk of HIV-1 infection, is that there are specific host genetic characteristics that will be associated with a lower risk of HIV-1 infection in exposed individuals from diverse populations infected with different strains of HIV-1. The primary outcome measure for this analysis will be subsequent HIV-1 infection, defined as above, and HLA class I allelic genotype. Based upon this initial analysis of the HIV-1 class I alleles and upon data from other ongoing studies, we propose to consider expanding this analysis to include assessment of HLA Class II alleles and co-receptor genotyping.

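### Sub-study 034B: counting any ELISPOT response within 12 months, by eventual infection status, biases the primary comparison when responses come and go

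*Supplement*

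**What the plan says.** 034B 6.3 forms two groups by eventual infection status. The exposure it contrasts is given in these words: "cohort and compared with respect to the presence or absence of any prior detectable immune response as measured by Elispot".

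034B 6.3.1 makes the exposure concrete: "our initial analysis will compare HIV-infection with a positive response to any gag peptide, at any time point within 12 months since enrollment". It adds: "Study participants will be expected to have multiple ELISPOT assays within the first 12 months of follow-up". The word prior does not appear in 6.3.1.

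034B 5.1.1 sets the outcome as "subsequent HIV-1 infection within the first 2 years of follow-up" and states the hypothesis that responders are at lower risk.

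034B 4.3.5 justifies frequent draws because "epitope recognition seen in exposed uninfected individuals may be transient and variable".

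On sampling, 3.1 requires: "Willing to permit phlebotomy of four tubes of blood every three months for 24 months". Appendix A, Table 1 stores PBMC at months 0, 3, 6, 9 and 12 and onward, with an HIV test at each visit. It has no separate ELISPOT row, so five assays in the first year is the most the schedule permits, not a stated number.

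**The concern.** The exposure window (12 months) lies inside the outcome window (2 years), and the groups are defined by what happens later. Under 6.3, someone infected at month 4 can contribute only the month-0 and month-3 assays, while someone never infected can contribute five. Unless response is a fixed trait, the chance of ever being positive rises with the number of assays. The uninfected then look more responsive even if response has no bearing on risk, and the error runs in the direction of the hypothesis. Under 6.3.1 read literally, assays after infection also count, and gag responses induced by the infection enter the exposure. This is the stated comparison for the first primary objective of 034B.

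**Working it through.** **The plan's sample sizes.** The 6.3.1 table gives totals of 238, 138 and 86 for differences of 20, 25 and 30 points. Neither response rates nor alpha are stated in 034B. I assume two-sided 0.05 (the level in 034A 6.3.1), 80% power and an uninfected:infected ratio k = 4 from the 20% seroconversion rate. Then

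n(infected) = [1.96·√(p̄(1−p̄)(1+1/k)) + 0.8416·√(p₁(1−p₁) + p₂(1−p₂)/k)]² / (p₁−p₂)², total = 5n.

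With p₁ = 0.60, p₂ = 0.85 and p̄ = (0.60 + 4×0.85)/5 = 0.80: [1.96×0.4472 + 0.8416×0.5214]² / 0.0625 = 27.7, total 138.4. For p₂ = 0.80 and 0.90 the totals are 238.5 and 84.7. The table is thus reproduced, within rounding, by a formula that treats response as one yes/no measured equally in both groups.

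**No-effect model.** Assumptions: constant hazard with 20% infected by month 24; assays at months 0, 3, 6, 9 and 12; positivity independent between visits and unrelated to infection; only pre-infection assays counted. The only prevalence in the document is 30-60% (034B 1.1), used here as the 12-month ever-positive rate E in the uninfected.

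Hazard: h = −ln(0.8)/24 = 0.0093 per month. Among the infected, the shares with 1, 2, 3, 4 and 5 qualifying assays are 13.8, 13.4, 13.0, 12.7 and 47.2%. The mean is 3.7 assays, against 5 in the uninfected.

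Per-assay positivity: q = 1 − (1−E)^(1/5). Ever positive with k assays: 1 − (1−q)^k.

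Example, E = 45%: q = 0.113; for k = 1 to 5, ever positive is 0.113, 0.213, 0.301, 0.380, 0.450. Weighted by the shares: 0.0155 + 0.0285 + 0.0392 + 0.0481 + 0.2124 = 0.344.

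| Uninfected ever positive | Infected ever positive | Spurious gap | Odds ratio |
|---|---|---|---|
| 30% | 22-23% | 7.5 points | 0.68 |
| 45% | 34% | 11 points | 0.64 |
| 60% | 47% | 13 points | 0.59 |

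**Type I error (simulated two-sided z-test, nominal 5%).**

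- N = 138: about 10-25% over the 30-60% range, nearly all toward protection.
- N = 100 (the 20 infections in the text divided by 0.20): 9-19%.
- N = 20-30: about 3-11% across the scenarios tried. Section 6.3 sets a minimum of 20. Section 2.3 expects 10-15 a year, so 20-30 over the two enrolment years given in 034A 4.2. Infections: 20×0.20 = 4 to 30×0.20 = 6.

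**Sensitivity to persistence.** At 20% positivity per assay, within-person correlation of 0.3 leaves a gap of about 8 points and about 12% type I error at N = 138; correlation of 0.5 leaves about 5 points and 7%. A response fixed from enrolment gives no gap.

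**Without the word prior.** Count all five assays, with 30-80% of post-infection assays positive (assumed). Ever positive becomes 48-65% in the infected against 30% in the uninfected, or 67-80% against 60%. The bias now points to harm.

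**The repair under the same model.** A single enrolment assay gives type I error of 4.4% at N = 138 and 5.0% at N = 100. Status so far, compared at each visit among those still at risk (log-rank-type score test), gives 4.6-5.0% and 4.1-5.2%.

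**The case against.** Several points on the other side stand. The bias depends on responses changing over time, and 4.3.5 says only that they may. Infections after month 12 are unaffected. Full independence between quarterly assays in one person is the extreme case. N = 138 is a table row that no enrolment projection approaches; at 20-30 participants, false positives stay close to nominal, and with Fisher's exact test they are 1.7-3.4% at N = 20 and 3.3-6.9% at N = 30.

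A reader might go further and infer that the artefact equals the 25-point design effect. At 20% positivity per assay it does reach 26 points (67% against 41%), but only if the infected group is limited to year-1 infections; 5.1.1 counts two years, where the same model gives 14 points (67% against 53%) and 29% type I error at N = 138. That scenario also puts 67% of the uninfected ever positive, outside the 30-60% in 1.1. Nor do the documents say that sampling stops at infection: Appendix A schedules PBMC to month 36, and the cut-off comes only from the word prior.

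It can also be said that the any-time rule is introduced for sizing and that no separate analysis plan is shown. But 6.3.1 calls it the initial analysis, and 6.3 gives the any-prior comparison independently. The point is a stated rule that misleads, not an omitted detail.

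**Conclusion.** The comparison is biased under either reading whenever responses are transient or acquired. With prior, it leans toward the sub-study's own hypothesis; without it, the opposite way. The plausible size is 8-13 points with independent assays, smaller with correlated ones, and zero only for a fully stable response. These figures rest on an assumed constant hazard over 24 months, up to five assays, and 30-60% ever positive. The documents do not support saying that the comparison must show protection, or that this small sub-study will probably report a false positive. The practical harm is a shifted estimate at any sample size. Section 6.3 of 034A, the companion sub-study, foresees pooling with other protocols; pooling or larger enrolment here would tighten the interval around the wrong value.

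**What to change.** Reconcile 034B 6.3 and 6.3.1 so that both count only ELISPOT assays taken at or before the participant's last negative HIV test. That alone does not equalise the number of assays, so also define the exposure in one of two ways:

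1. the enrolment (month 0) result; or
2. ELISPOT status updated at each visit among those still at risk, analysed by a person-time or log-rank-type comparison, kept simple because only about 4-6 infections are expected.

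The cost is mainly wording, since month-0 PBMC storage and HIV tests at every visit are already in Appendix A. A month-0 exposure will find fewer responders than repeated assays and requires the stored month-0 cells to be assayed. The time-updated version uses the repeated draws that 4.3.5 argues for, but will be imprecise with so few events.
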